Clinical Investigation Plan

CP326

Exploratory study of a new urine collection device for men

June 2020 – December 2020

1st of December 2020

NCT04672993|

This confidential document is the property of Coloplast A/S.
No unpublished information contained herein may be
disclosed without written approval of Coloplast A/S.

CONFIDENTIAL

Page 1 of 34

CHANGE LOG

VER-SION NUM-BER	ISSUED BY (INITIALS)	COMMENTS (MAJOR CHANGES SINCE LAST REVISION)
1.0	[name]	First approved version
2.0	[name]	
Updated due to comments from Ethics Committee and minor internal changes
 
Section 1.1 – Sponsor representatives: Contact information for Data manager and Clinical Manager have been updated.
 
Section 6.2 – Recruitment and enrolment: Only potential subjects in the Coloplast Database, that have consented to be contacted regarding clinical investigations, will receive an invitation letter.
 
Section 7.3 – Flow-charts: Some answers have been updated to be clearer.

CONFIDENTIAL

Page 2 of 34

SYNOPSIS OF THE CLINICAL INVESTIGATION

The aim of the study is to evaluate the subjects experience of the test product "Contend Protective Cover" - a urine collection device for males.

Objective

Primary objective:

- To investigate the comfort of using the test product.

Secondary objective:

- To evaluate handling and subject experience during wear in support of commercial claims.

Design of the investigation

An open-labelled, single arm study design was chosen for study CP326.

A single arm study over a duration of 1 week + up to 3 days extra

V0: Inclusion

V1: Test visit 1

V2: Test visit 2 and termination

Subjects may be interviewed up to two times either in-person or over the phone and these interviews will preferably be conducted at V2. Second interview can be conducted up to 6 months after V2.

Primary endpoint and secondary endpoint(s)

Primary endpoint:

- Frequency of success in support of "comfortable"

Secondary endpoints:

- Frequency of success in support of various commercial claims

Please see [Table 2](#) for a detailed listing of all endpoints

Population/subjects

Twenty male subjects who are suffering from mild-to-moderate urinary incontinence, will be enrolled in this study.

To be included in the investigation, the subjects must comply with the selection criteria described below

Inclusion criteria:	Exclusion criteria
1. Have given written informed consent 2. Male	1. If experiencing incontinence less than once per week

CONFIDENTIAL

Page 3 of 34

 3. Be at least 18 years of age and have full legal capacity 4. Suffering from urinary incontinence equivalent to using up to 6 pads or 2 diapers per day 5. Have had current incontinence issues for at least 3 months 6. Able to understand patient information and able to change the product himself 7. Up to 6 of the subjects can be user who are using an intermittent catheter due to retention, but who are also dribble incontinent in-between catheterizations, and hence need a product to handle the incontinence. 8. Able to fit the test product. 	
 2. Bedridden, using wheelchair or using a walking aids daily.
--	---

Test products and comparator

The test product "Contend Protective Cover" is a leak tight pocket with an absorption material to be placed on the penis. The test product is a single use device which and should be changed when needed and minimum after 24h. 2 sizes will be tested: regular fit (Ø18) and large fit (Ø22).

The test product will be CE-marked prior to study start.

Investigation approval

The investigation will be approved by the Ethical committees in Denmark before initiation of the investigation.

LIST OF ABBREVIATIONS

ABBREVIATION	WRITTEN OUT	EXPLANATION
ADE	Adverse Device Effect	See section 16.2
AE	Adverse Event	See section 16.1
ASADE	Anticipated Serious Adverse Device Effect	See section 16.4.2
CFR	Code of Federal Regulation	
CIP	Clinical Investigation Plan	
CRF	Case Report Form (paper or electronic)	Questionnaire to be used for data collection. See section 10.1
CM	Clinical Manager	
CRO	Clinical Research Organisation	See section 6.2
EC	Ethics Committee	
EDC	Electronic Data Capture	A software system designed for collecting clinical data in clinical trials. It consists of a data base for each clinical trial.
FDA	Food and Drug Administration	
IFU	Instruction For Use	
ITT	Intention to Treat	
PI	Principal Investigator	Qualified person responsible for conducting the clinical investigation at an investigation site. If the clinical investigation is conducted by a team of individuals at an investigation site, the PI is the responsible leader of the team. Whether this is the responsibility of an individual or an institution can depend on national regulations.
PP	Per Protocol	
SADE	Serious Adverse Device Effect	See section 16.4.1
SAE	Serious Adverse Event	See section 16.4
USADE	Unanticipated Serious Adverse Device Effect	See section 16.4.3

CONFIDENTIAL

Page 5 of 34

1.2. Investigators

The CM is responsible for maintaining an updated list of all Principal Investigators (PI's), investigation sites and institutions.

PRINCIPAL INVESTIGATOR

Visits will be conducted at subject's own home or at a clinic or at Coloplast A/S, if subjects prefer not to have visits at own home.

CONFIDENTIAL

Page 9 of 34

2. Introduction

The prevalence of urinary incontinence in adult men has been estimated to range between 11-34% in older men, and 3-5% in younger and middle-age men [1]. The products available for men with mild-to-moderate incontinent are typically adult pads or diapers, e.g. Tena for men. Pads and diapers are not always optimal, as they are seen as large/bulky to use and store, and there is a risk of leakage, if the pad/diaper displaces during use, and urinary leaks are not absorbed by the product.

Coloplast has developed a new product for men with mild-to-moderate urinary incontinence, which is placed directly on the penis, and where the absorber (pad) are placed in a water-tight pocket. The product is the size of the smallest incontinence pads on the market for men, and can fit into to pockets of most trousers.

3. Objective(s) and hypotheses of the clinical investigation

3.1. Objective (s)

The aim of the study is to evaluate the subjects experience of the test product "Contend Protective Cover" - a urine collection device for males.

The primary objective is:

- To investigate the comfort of using the test product.

Secondary objectives are:

- To evaluate handling and subject experience during wear in support of commercial claims.

3.2. Hypotheses

[figure not shown]
There is no formal hypotheses associated to this study.

The study will provide valuable insight into the use of the device in an everyday life setting.

4. Design of the clinical investigation

4.1. General

An open-labelled, single arm study design was chosen for study CP326 with a duration of 1 week + up to 3 days extra as illustrated below.

V0: Inclusion, V1: Test visit 1,

V2: Test visit 2 and termination

Subjects may be interviewed up to two times either in-person or over the phone and these interviews will preferably be conducted at V2. Second interview can be conducted up to 6 months after V2.

CONFIDENTIAL

Page 10 of 34

4.2. Endpoints and assessments

Primary and secondary endpoints are mentioned in this section on a high level. Endpoint details and flow-chart of measures are presented in [Table 2](#).

4.2.1. Primary endpoint

Primary endpoint:

- Frequency of success in support of "comfortable"

4.2.2. Secondary endpoints

Secondary endpoints:

- Frequency of success in support of various commercial claims

Please see [Table 2](#) for a detailed listing of all endpoints

4.2.3. Rationale for selection and measurement of endpoints

The endpoints selected for this study have been chosen to provide the information about the subjects' experience with the product. Information about comfort, handling and experience during wear are all important in understanding how the subjects use and evaluate the product.

4.2.4. Demography and potential compromising factors

Assessments:

- Age
- Level of incontinence (how often, how much)
- Usual product/management routine (using a product, what type, how many)
- Reason for incontinence (if known)
- Duration of incontinence (for how long has subject had the current issues)

4.3. Discussion of clinical investigation design

An open-labelled, single arm study design was chosen for this study with a duration of a test period of 1 week. The study cannot be blinded because only one test product is tested. The study period of one week is assessed as adequate for evaluation of the endpoints.

5. Investigational device and comparator(s)

5.1. Description of investigational device

The test product is a leak tight pocket containing an absorber to absorb urinary leaks, to be placed on the penis. The test product is a single use device which should be changed when needed and minimum after 24h. 2 sizes will be tested: regular fit (Ø18) and large fit (Ø22). The test product will be CE-marked prior to study start.

Figure 1: Investigational device

Subjects will be provided with a sufficient number of test devices

The turquoise line on the front side of device on the picture to the left, mark the pocket opening to be used when peeing while wearing the device. Back side of the device (facing the body) on the picture to the right, show the transparent flex collar, fixating the device on the penis.

5.1.1. Manufacture

Coloplast A/S, [name], is the manufacturer of the CE marked test Product.

5.1.2. Identification, traceability and labelling of the device

The investigational test device will be identified as Contend Protective Cover.

Investigational device label Ref [3] can be found in IFU Ref [4]

5.2. Purpose of the device in the clinical investigation

The purpose of the device is to collect and contain urine from a male subject suffering from mild-to-moderate incontinence.

5.3. Intended population for the device

Males who are suffering from mild-to-moderate urinary incontinence once a week, are considered intended population for the device.

5.4. Handling and training

The handling of the test products is described in details in the Instruction for Use (IFU), which is included in all boxes with test products. Storage conditions are also stated in the IFU.

All Investigators / investigator representatives will receive training by sponsor / investigator in the handling and correct use of the test products. The Investigator/investigator representative will train the subjects in the correct use of the test products.

5.5. Ethical considerations, investigational device and clinical investigation risks and benefits

The clinical investigation is conducted in accordance with current law and applicable standards see section 14. The rights, safety and well-being of human subjects shall prevail over interest of science and society.

No risks are expected to the subjects other than the adverse events mentioned here, all of which are well known in connection with the use of absorbent product for urinary incontinence. Please see section 16.2. The risk assessment of the test products is carried out in accordance with the requirements of ISO 14971: 2007.

To mitigate and reduce risks, all subjects will be trained, according to the IFU, in the use of the product.

Expected benefits are a better fitted and more discreet product, tailored for men with mild-to-moderate urinary incontinence.

Disadvantages during the investigation could be the extra workload related to completion of questionnaires, visits at home or at a clinic or at Coloplast A/S, if subjects prefer not to have visits at own home.

5.6. Comparator product(s)

There is no comparator product in this investigation.

6. Subjects

Twenty male subjects who are suffering from mild-to-moderate urinary incontinence, will be enrolled in this study.

6.1. Inclusion and exclusion criteria

To be included in the investigation, the subjects must comply with the selection criteria described below

Inclusion criteria:	Justification:

1. Have given written informed consent2. Male3. Be at least 18 years of age and have full legal capacity4. Suffering from urinary incontinence equivalent to using up to 6 pads or 2 diapers per day5. Have had current incontinence issues for at least 3 months6. Able to understand patient information and able to change the product himself7. Up to 6 of the subjects can be users who are using an intermittent catheter due to retention, but who are also dribble incontinent in-between catheterizations, and hence need a product to handle the incontinence.8. Able to fit the test product.	
1. To meet the Helsinki Declaration2. To meet the target population of this device3. To meet the Helsinki Declaration4. To meet the target population of this device5. To be sure subjects meets target population of this device6. To meet the Helsinki Declaration7. To meet the target population of this device8. To meet the target population of this device

CONFIDENTIAL

Page 13 of 34

Exclusion criteria:	Justification:

 1. If experiencing incontinence less than once per week 2. Bedridden, using wheelchair or using a walking aids regularly 	
 1. To meet the target population of this device 2. To meet the target population of this device

6.2. Recruitment and enrolment

Recruitment of potential subjects will begin once approval has been obtained from Ethics Committee.

Recruitment method	Coloplast Database	Advertisement	Patient records
Potential subjects	
Recruitment will go through Coloplast own subject database (Intermittent Catheterization users) in Denmark. Potential subjects are identified by the following searching criteria in the Coloplast database:
 
 • Has consented to be contacted regarding clinical investigations • Using Intermittent Catheterization • Male • Be at least 18 years of age 	
Advertisement i.e. in local shops, sports facilities, local newspapers, social media and patient associations. The advertisement will state the contact info of investigator or delegated study personnel to contact. A CRO may help by receiving reply letters-mails and/or answering the phone from interested subjects.
	
Recruitment from hospitals, home care nurses and outpatient urology clinics will be via patient visit or screening of subject records kept at the participating sites. Only contact information regarding potential subjects who are assessed eligible will be passed on.

First contact	The identified potential subjects will as first contact be sent an Invitation and Reply Letter by mail or email.	Interested subject contact the investigator or delegated study personnel	The identified potential subjects will be contacted and informed about the investigation by the investigator or delegated study personnel (First contact will be by letter or email, a follow-up contact can be via telephone, letter or email).
	If a potential subject does not return the reply letter or answer the email, they may be contacted by phone, mail or email to make sure that they have received the approach.		
Second contact	
If potential subjects return the Reply Letter/reply to the email, or have called the investigator as first contact and are interested, the Investigator or delegated site personnel will contact the subjects by phone and give a short introduction to the investigation and go over the inclusion and exclusion criteria.
 
If the subjects do not meet the inclusion criteria or meet the exclusion criteria, this will be registered in the Subject Screening Log.
		
Subject Information Form	
If subjects are eligible and interested in participating, then written information about the investigation (subject information) will be sent to the subjects to ensure that they are given the opportunity to read about the investigation before a possible information visit, and so that they can prepare any possible questions they may have.
 
Information visit V0 will be booked at this point and the subjects are instructed to contact the investigator or delegated study personnel if they, after having read the subject information, no longer are interested in participation in the study.
		

CONFIDENTIAL

Page 14 of 34

First visit Information visit	If an eligible subject is interested in participating, information visit (V0) will be arranged in a room ensuring quiet surroundings. That could either be in the subject own home or at a clinic or at Coloplast if subject prefer not to have visits in own home. When arranging the visit, it will be ensured, that the subject has received the Subject Information prior to the visit. The subjects will receive both written and verbal information about the possibility of bringing a companion to the informational visit and to any possible subsequent visits. See section 15 for information to be given to the subjects, as well as the informed consent process.
Enrolment and inclusion visit (V0)	The subjects have the right to wait 24h before deciding on participation. If/when the subject decides to participate the subject will be asked to sign the relevant forms (see section 13). If a subject so desires, and it is certain that it is understood what the investigation entails and the relevant forms have been signed the subjects are considered enrolled in the investigation.

6.3. Subject withdrawal criteria

The subject can withdraw from the investigation at any time for whatever reason without any consequences for their future treatment outside the clinical investigation. Investigator may withdraw a subject from the investigation at any time if they judge it to be the subject's interest.

The investigator must withdraw a subject from the investigation due to:

- Non-compliance with the CIP impacting the scientific integrity of the investigation
- If subject's safety and wellbeing is compromised by further participation.

Withdrawn subjects will not be replaced by new subjects.

A subject who is withdrawn from the investigation, for any reason, will be encouraged to contact the investigator if problems arise that the subject believes are related to the clinical investigation. Subjects who have not experienced any adverse events will not be followed up. For subjects who experience adverse events, see section 16.

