7.1.1. Visits

Visit 0 (Inclusion visit)

If a potential subject is interested in participating after the first contact, a visit (visit 0) will be arranged at subject's home or at a clinic or at Coloplast, if subjects prefer not to have visits in own home, in a room reserved to ensure privacy and quiet surroundings. When arranging the visit, it will be ensured, that the subject has received the Subject Information Form prior to the visit. The subjects will receive both written and verbal information to ensure that the subject understands what was read and explained and can freely agree to participate in the investigation. The subject will, beforehand, also be informed about the possibility of bringing a companion to Visit 0 and to any possible subsequent visits. During the visit the principal Investigator, or delegate, will provide oral information about the investigation based on the Subject Information Form. The subject has the right to wait before deciding on participation.

If/when subjects decide to participate, they will be asked to sign the Informed Consent Signature Form. If a subject so desires, and it is certain that it is understood what the investigation entails, and the relevant form has been signed, the subjects are considered enrolled in the investigation. Enrolled subjects that are deemed eligible per the inclusion/exclusion criteria are allocated a subject number. Visit 0 and visit 1 can be combined.

Visits 1 (V1)

During visit 1, part 1 of the questionnaire Table 1 (demographic questions) will be completed by the Principal Investigator, or delegate. The subject will be trained in the use of the test product per IFU. The subjects are instructed to continue their everyday life and change test product whenever they feel the need to.

Visits 2 (V2)

During visit 2, the Principal Investigator, or delegate will ensure part 2 of the questionnaire [Table 2](#) will be completed by subjects. Potential (S)AE's will be captured by the Principal Investigator, or delegate. Hereafter termination If appropriate, subjects may be interviewed regarding use of the test product by a Coloplast representative at V2, otherwise an alternative time for interview may be scheduled.

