9.1. Statistical design, method and analytical procedures

Endpoints and assessments

All baseline assessments, endpoints and other measurements will be reported by descriptive statistics and/or listed.

Analysis populations

Intention to Treat (ITT), Safety and Per Protocol (PP) populations will be defined at a formal data review meeting just before database lock. As a minimum, the clinical manager and the statistician will be involved in the classification of subjects.

The Safety population (basis for the AE summary) will constitute subjects with valid informed consent.

The ITT population (Full analysis set) will constitute all subjects, with valid informed consent, who have been exposed to at least one product and furthermore, with information recorded on at least one endpoint (non-missing).

No formal PP population is planned. However, if additional explorative analyses are deemed necessary, a PP population will be established, based on a subset of the ITT population.

Individual endpoints/data points may be excluded from analysis, even though the corresponding subject belongs to the ITT population. This situation could arise due to protocol violations, where, at one visit, the primary endpoint could be affected, but same effect did not occur at the following visit.

All analysis will be based upon the ITT population and AEs will be summarized based on the safety population.

Any exclusion of subjects or data points from any of the populations must be documented.

Descriptive statistics for continuous variables are presented with N, Mean, SD (standard deviation), Median, Min and Max), where N denotes the number of subjects contributing with non-missing data. For discrete variables, descriptive statistics are presented with N and percentage, where percentage is based on the total number of subjects/observations with non-missing data.

A significance level of alpha equal to 0.05 (two-sided) is applied.

All endpoints will be analyzed by an exact test in the binomial distribution (proportion is equal to 50%), where the frequency of success or will estimated with 95% confidence limits.

The two highest or best categories in questions obtained from a 5-point ordinal scale is defined as a success. Likewise, the answer yes, is defined a success, obtained from questions with a yes/no categorical option.

In favor of a claim, the lower 95% confidence limit must be above 50%.

Other summaries and analyses can be made, if relevant.

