9.2. Sample size

Due to the conceptual nature of this trial no formal sample size calculation has been performed. It is assumed that 20 subjects will be adequate for evaluating the comfortability of the test product.

We strive to include subjects representing most possible age groups in the study.

Due to the exploratory nature of the study, drop-out subjects will not be replaced.

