9.3. Level of significance and power

If a statistical analysis is performed a significance level of 5% will be applied. As this is an exploratory study no power has been applied.

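### A man who leaves before V2, including by mandatory withdrawal for undefined non-compliance, is never asked about comfort and drops out of the ITT analysis; at n = 20 two such losses can change the result

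*Combined protocol and SAP*

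**What the plan says.** **Withdrawal (Section 6.3).** Two grounds make withdrawal compulsory. One is "Non-compliance with the CIP impacting the scientific integrity of the investigation"; the other is compromised safety or wellbeing. A man may also leave voluntarily at any time. The first ground has no threshold, example or adjudication step. The section adds "Withdrawn subjects will not be replaced by new subjects" and provides no follow-up for withdrawn men who had no adverse event. It specifies no exit questionnaire.

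**Endpoint collection (Section 7.1.1, Tables 1 and 2).** Part 2 of the questionnaire, which carries the comfort item and all other endpoints, is completed at V2 only. Between V1 and V2 men carry on with daily life and "change test product whenever they feel the need to". No minimum wear is set.

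**Analysis (Sections 9.1 and 9.4).** The ITT set needs valid consent, exposure to at least one product and at least one non-missing endpoint. Percentages use non-missing data. Section 9.1 also says "Individual endpoints/data points may be excluded from analysis, even though the corresponding subject belongs to the ITT population", and gives as its reason a protocol violation that affects the primary endpoint at one visit but not at the next. Success on a five-point item is either of the two best categories. A claim is supported when the lower 95% confidence limit exceeds 50%.

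**Size (Sections 6, 9.2 and 9.3).** "Twenty male subjects who are suffering from mild-to-moderate urinary incontinence, will be enrolled in this study"; "no formal sample size calculation has been performed"; "As this is an exploratory study no power has been applied".

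**The concern.** The study has one endpoint visit, about a week after the product is handed out, and no way of collecting an answer from a man who leaves before it. Such a man is not counted as a failure. He disappears from numerator and denominator alike, and 9.1 has no rule for him.

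Discomfort, poor fit and leakage are plausible reasons for a man to leave, and they are close to what the endpoints measure. If leaving is related to the answer he would have given, the men who remain are a favourable selection. The compulsory non-compliance ground adds to this because an open-label investigator must interpret an undefined term case by case.

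At stake are the primary comfort endpoint and the secondary claims judged by the same rule. With 20 men, that rule can turn on one or two answers.

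**Working it through.** The plan states no power, expected success rate or expected withdrawal rate, so it has no figure of its own to reproduce. The check applies its claim rule with men removed.

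**Inputs.** n = 20 (Section 6). Null proportion 50%, exact binomial test, and "A significance level of alpha equal to 0.05 (two-sided) is applied" (Section 9.1). Pass if the lower 95% limit is above 50% (Sections 9.1 and 9.4). Denominator: non-missing answers (Section 9.1).

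**Formula.** For x successes among n answers, the exact (Clopper-Pearson) lower limit is L(x, n) = the 2.5% quantile of Beta(x, n − x + 1). L exceeds 50% exactly when P(X ≥ x | n, 0.5) is below 0.025.

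Hand check for n = 20, x = 15: (15504 + 4845 + 1140 + 190 + 20 + 1)/1048576 = 21700/1048576 = 0.0207, so 15/20 passes. For x = 14, add 38760: 60460/1048576 = 0.0577, so 14/20 fails.

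**Step 1: remove only men who would have answered below the success categories.**

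| All 20 answer | L | After loss of dissatisfied men | L | Result |
|---|---|---|---|---|
| 14/20 | 45.7% (fail) | 14/19 (one lost) | 48.8% | fail |
| 14/20 | 45.7% (fail) | 14/18 (two lost) | 52.4% | pass |
| 13/20 | 40.8% (fail) | 13/17 (three lost) | 50.1% | pass |
| 12/20 | 36.1% (fail) | 12/15 (five lost) | 51.9% | pass |

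**Step 2: remove a satisfied man.** 15/20 passes (50.9%). Losing one success gives 14/19, which fails (48.8%).

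**Step 3: chance of passing.** Let p be the true success rate, f the share of would-be failures lost before V2 and s the share of would-be successes lost. Each man is a recorded success with probability a = p(1 − s), a recorded failure with probability b = (1 − p)(1 − f), and lost with probability 1 − a − b. The chance of passing is the multinomial probability, over 20 men, of all outcomes with L above 50%. The documents give none of p, f or s; the values below are assumptions chosen to show a range.

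| p | No loss | f = 20%, s = 0 | f = 30%, s = 0 | f = 20%, s = 10% | f = s = 10% |
|---|---|---|---|---|---|
| 50% | 0.021 | 0.046 | 0.076 | 0.028 | 0.016 |
| 70% | 0.416 | 0.508 | 0.592 | 0.402 | 0.329 |

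For scale: at p = 50% and f = 20%, s = 0, the expected loss is 20 × 0.5 × 0.2 = 2 men, and the expected success rate among those who answer is about 0.5/0.9 = 55.6%.

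**Step 4: count exposed men with no Part 2 as non-successes.** If all 20 were exposed, n stays 20 and 15 successes are needed. The 14/18 of Step 1 goes back to 14/20 and fails. At a true rate of 50% the chance of passing is then at most 0.0207, whatever the pattern of loss.

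**The case against.** **Low wear is not shown to be non-compliance.** A reader might infer that 6.3 ejects men who wear the device too little. The documents do not say so. There is no wear requirement to breach, and 6.3 covers only non-compliance that affects scientific integrity. Table 1 schedules no contact between V1 and V2, and wear is asked about in the V2 questionnaire itself. This stands. Non-use could still surface before Part 2 is answered, through the device accountability records in Section 13 or the phone visits mentioned in passing in 7.1, and nothing in 6.3 tells the investigator how to treat it.

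**There is no contradiction with 9.1.** A reader might infer that 6.3 removes the same man whom 9.1 retains. But a man withdrawn before V2 has no recorded endpoint, so he falls outside the ITT set by 9.1's own definition. The sentence on individual data points permits a violator's data to be left out; it does not guarantee that they are analysed. This also stands. What remains is a tension: 9.1 pictures a violator continuing to another visit within the ITT set, while 6.3 may end his participation.

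**The direction of bias is not established.** This stands too. Step 2 and the last column of Step 3 show that losing satisfied men, or losing both kinds equally, works against the claim. At p = 70% even the mildly unequal pattern (20% and 10%) slightly lowers the chance of passing. No figure in the documents suggests that two or three men would be withdrawn for non-compliance.

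**The investigator does not choose the analysis set.** A reader might infer that the estimate becomes a per-protocol one picked by the investigator. Section 9.1 gives the classification to a data review meeting that includes at least the clinical manager and the statistician, and requires exclusions to be documented. That meeting cannot, however, restore an answer that was never collected.

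**Other exits matter more.** Voluntary and safety or wellbeing withdrawals are more direct routes for an uncomfortable man to leave. This is right, and is why the fix should cover every early exit.

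**Conclusion.** The concern holds in a limited form. The plan has a gap in data collection: any exit before V2 loses the comfort answer and removes the man from the ITT denominator, and one compulsory ground for exit is undefined and left to the investigator's judgement. If two dissatisfied men are lost from 14/20, or three from 13/20, a failed claim becomes a pass. With a true rate of 50%, losing 20% to 30% of would-be failures and no would-be successes raises the chance of a false claim from 0.021 to between 0.046 and 0.076.

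These sizes rest on two assumptions that the documents neither support nor exclude: that some men leave before V2, and that those who leave are mainly dissatisfied. The result is a risk of inflation, not a demonstrated upward bias. Sections 6.3 and 9.1 should be aligned, but they do not directly contradict each other. For an exploratory study of 20 men this is an inexpensive improvement, worth making because the pass rule is fragile and supports commercial claims.

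**What to change.** **Section 6.3.** State that stopping or reducing wear of the product is recorded as a deviation and is not in itself non-compliance that requires withdrawal. State that any man exposed to at least one product who leaves early, whether voluntarily, for non-compliance or for safety or wellbeing, is asked to complete Part 2 at exit if he agrees, rating the product on the use he had. Leave the safety and wellbeing ground unchanged. The non-compliance ground need not be deleted.

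**Section 9.1.** State that Part 2 answers given at early exit are included in the ITT analysis. Add a sensitivity analysis that counts exposed men with no Part 2 as non-successes, reported beside the main result for each claim.

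**Cost.** Protocol wording, one questionnaire at exit for the men concerned, and one further tabulation. Some ratings will rest on short wear, and the success frequency may come out slightly less favourable. The sensitivity analysis is deliberately conservative, because a lost man who was satisfied also counts against the claim.
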